8.3.5 ADVERSE EVENT REPORTING

8.3.6 SERIOUS ADVERSE EVENT REPORTING

The study clinician will immediately report to the sponsor any serious adverse event, whether or not considered study intervention related, including those listed in the protocol or investigator brochure and must include an assessment of whether there is a reasonable possibility that the study intervention caused the event. Study endpoints that are serious adverse events (e.g., all-cause mortality) must be reported in accordance with the protocol unless there is evidence suggesting a causal relationship between the study intervention and the event (e.g., death from anaphylaxis). In that case, the investigator must immediately report the event to the sponsor.

All serious adverse events (SAEs) will be followed until satisfactory resolution or until the site investigator deems the event to be chronic or the participant is stable. Other supporting documentation of the event may be requested by the Data Coordinating Center (DCC)/study sponsor and should be provided as soon as possible.

The study sponsor will be responsible for notifying the Food and Drug Administration (FDA) of any unexpected fatal or life-threatening suspected adverse reaction as soon as possible, but in no case later than 7 calendar days after the sponsor's initial receipt of the information. In addition, the sponsor must notify FDA and all participating investigators in an Investigational New Drug (IND) safety report of potential serious risks, from clinical trials or any other source, as soon as possible, but in no case later than 15 calendar days after the sponsor determines that the information qualifies for reporting.]

8.3.7 REPORTING EVENTS TO PARTICIPANTS

Participants will be informed about AEs and SAEs, and study-related results on an individual or aggregate level. Incidental findings associated with study procedures will be monitored by the primary investigator and reported appropriately as required.

8.3.8 EVENTS OF SPECIAL INTEREST

8.3.9 NREPORTING OF PREGNANCY

Should a participant become pregnant during the study, the primary investigator will create a plan to stop or taper the study drug as quickly as possible. The primary investigator will communicate with the physician managing the pregnancy and the subject and pregnancy will be followed to term.

8.4 UNANTICIPATED PROBLEMS

8.4.1 DEFINITION OF UNANTICIPATED PROBLEMS (UP)

The Office for Human Research Protections (OHRP) considers unanticipated problems involving risks to participants or others to include, in general, any incident, experience, or outcome that meets all of the following criteria:

- Unexpected in terms of nature, severity, or frequency given (a) the research procedures that are described in the protocol-related documents, such as the Institutional Review Board (IRB)-approved research protocol and informed consent document; and (b) the characteristics of the participant population being studied;
- Related or possibly related to participation in the research (“possibly related” means there is a reasonable possibility that the incident, experience, or outcome may have been caused by the procedures involved in the research); and
- Suggests that the research places participants or others at a greater risk of harm (including physical, psychological, economic, or social harm) than was previously known or recognized.

8.4.2 UNANTICIPATED PROBLEM REPORTING

The investigator will report unanticipated problems (UPs) to the reviewing Institutional Review Board (IRB) and to the Data Coordinating Center (DCC)/lead principal investigator (PI). The UP report will include the following information:

- Protocol identifying information: protocol title and number, PI's name, and the IRB project number;
- A detailed description of the event, incident, experience, or outcome;
- An explanation of the basis for determining that the event, incident, experience, or outcome represents an UP;
- A description of any changes to the protocol or other corrective actions that have been taken or are proposed in response to the UP.

To satisfy the requirement for prompt reporting, UPs will be reported using the following timeline:

- UPs that are serious adverse events (SAEs) will be reported to the IRB and to the DCC/study sponsor within 24 hours of the investigator becoming aware of the event.
- Any other UP will be reported to the IRB and to the DCC/study sponsor within <insert timeline in accordance with policy> of the investigator becoming aware of the problem.
- All UPs should be reported to appropriate institutional officials (as required by an institution's written reporting procedures), the supporting agency head (or designee), and the Office for Human Research Protections (OHRP) within <insert timeline in accordance with policy> of the IRB's receipt of the report of the problem from the investigator.]

8.4.3 REPORTING UNANTICIPATED PROBLEMS TO PARTICIPANTS

Unanticipated problems affecting the study or study participants will be reported to subjects by the primary investigator as soon as they are known.

9 STATISTICAL CONSIDERATIONS

9.1 STATISTICAL HYPOTHESES

State the formal and testable null and alternative hypotheses for primary and key secondary endpoints, specifying the type of comparison (e.g., superiority, equivalence or non-inferiority, dose response) and time period for which each endpoint will be analyzed.

- Primary Efficacy Endpoint(s): the study will attempt to demonstrate the improvement in mean average from baseline to final visit of both corneal staining and subjective ocular discomfort as measured by the OSDI scale. Ed
- Secondary Efficacy Endpoint(s): improvement in mean average from baseline to final visit of conjunctival lissamine green staining. The study will demonstrate no change in baseline to final intraocular pressure, no worsened BCVA, and stable slit lamp biomicroscopy and dilated fundus exams.

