9.2 SAMPLE SIZE DETERMINATION

This is a small pilot study of 12 participants completing the study assessments. There is no placebo and it is not powered to show statistical significance.

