9.3 POPULATIONS FOR ANALYSES

- *Intention-to-Treat (ITT) Analysis Dataset (i.e., all randomized participants)*
- *Safety Analysis Dataset: defines the subset of participants for whom safety analyses will be conducted (e.g., participants who took at least one dose of study intervention)*

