9.4.3 ANALYSIS OF THE SECONDARY ENDPOINT(S)

For each secondary endpoint:

- *The improvement of conjunctival staining after lissamine green instillation in which discrete superficial punctate stains are counted.. Descriptive statistics will be used for intent to treat patients and safety populations who receive at least one dose of the study drug.*
- *IOPs will be analyzed for mm Hg increase from baseline, also noting 10 mm Hg increase from baseline. It will be measured at each visit. Descriptive statistics will be used for intent to treat patients and safety populations who receive at least one dose of the study drug.*

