9.4.4 SAFETY ANALYSES

Safety endpoints will be analyzed as summary statistics during treatment, coded as per Medical Dictionary for Regulatory Activities and counted once only for a given participant. Start/stop dates, severity as determined by the investigator, relationship, expectedness, outcome and duration will be reported. Adverse events leading to premature discontinuation from the study and serious treatment-emergent AEs will be presented separately in a listing.

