## Statistical Analysis Plan Acthar Pilot Study

The statistical analysis plan for this study includes analysis of patients completing the trial and measuring the change from baseline to final visit including intervisit changes. For each of these time points, P-values will be collected, standard deviations, standard error means, 95% confidence intervals of the difference and 2-tailed t test applied. There is no placebo or control in this study and the number of participants was not powered to show statistical differences.

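### Section 9.1 promises to show unchanged eye pressure, vision and eye examinations, which 12 uncontrolled participants with no margin and no power cannot show

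*Protocol*

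**What the plan says.** Protocol section 9.1 lists among its hypotheses: "The study will demonstrate no change in baseline to final intraocular pressure, no worsened BCVA, and stable slit lamp biomicroscopy and dilated fundus exams". The efficacy sentence just above it says only that the study will try to show improvement, so the safety sentence is the firmer promise. The template instruction in 9.1, which asks for testable hypotheses and the type of comparison (equivalence and non-inferiority are among its examples), is still in place and unanswered.

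The rest of the plan is more modest:

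- Section 9.2: 12 completers, no placebo, and "it is not powered to show statistical significance".
- Section 9.4.3: "IOPs will be analyzed for mm Hg increase from baseline, also noting 10 mm Hg increase from baseline", with descriptive statistics in the intent-to-treat and safety populations.
- Section 9.4.4: "Safety endpoints will be analyzed as summary statistics during treatment".
- Section 9.3: the safety dataset is described, by way of example, as "participants who took at least one dose of study intervention".
- SAP: "The statistical analysis plan for this study includes analysis of patients completing the trial", with p-values, "95% confidence intervals of the difference and 2-tailed t test applied". It names no variables and repeats that the study is unpowered.

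Sections 8.1 and 8.2 say how BCVA, slit lamp and fundus findings are recorded. Neither document says what counts as worsened or stable.

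**The concern.** A conclusion of no change needs a stated largest change that would still count as none, and a rule for comparing the data with it. Section 9.1 states the conclusion, but neither document supplies the margin or the rule. Nobody could say beforehand which results would meet the sentence and which would fail it, and a margin chosen after seeing the data could give either answer.

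This matters because section 2.3.1 lists cataracts and glaucoma among the known risks, and section 3 says the safety assessment must cover glaucoma, cataract and change in vision. Section 4.2 says the results may be the basis for a larger randomised study. A statement that safety was demonstrated could therefore be carried forward on data that only allow estimation.

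**Working it through.** The plan gives no power, SD, effect size or margin, and 12 is not derived from a calculation. There is no stated figure to reproduce. The checks below ask what 12 participants could show.

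**Inputs**

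- n = 12 completers (section 9.2).
- Two-tailed t test and 95% confidence interval (SAP). The 5% test level is taken to match that interval.
- The 10 mm Hg IOP flag (section 9.4.3).
- SD of IOP change from baseline: not in the documents. Assumed 2, 3 or 4 mm Hg.
- True mean rise of 2 mm Hg: also an assumption, for illustration.

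**1. Precision of a mean change**

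Half-width of the 95% CI = t(0.975, 11) × SD / √12 = 2.201 × SD / 3.464 = 0.635 SD.

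**2. Chance that a true rise is non-significant**

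The t statistic has a noncentral t distribution with 11 degrees of freedom and noncentrality (2 / SD) × √12. The probability of non-significance is P(|T| < 2.201).

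| Assumed SD (mm Hg) | 95% CI half-width (mm Hg) | Noncentrality | P(non-significant) |
|---|---|---|---|
| 2 | 1.27 | 3.464 | 0.117 |
| 3 | 1.91 | 2.309 | 0.442 |
| 4 | 2.54 | 1.732 | 0.647 |

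A real mean rise of 2 mm Hg would pass as non-significant in 12%, 44% or 65% of trials.

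**3. No participant reaching the 10 mm Hg flag**

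This check needs no SD. With 0 events in 12, the exact two-sided 95% upper limit solves (1 − p)^12 = 0.025:

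p = 1 − 0.025^(1/12) = 0.265 (26.46%, or 26% to the nearest whole per cent).

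The one-sided 95% limit is 1 − 0.05^(1/12) = 0.221. Conversely, if 10% of patients truly had such a rise, the chance of seeing none in 12 is 0.9^12 = 0.282.

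**4. Is there a criterion elsewhere?**

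- IOP: the 10 mm Hg flag has no allowed count and no link to the 9.1 sentence.
- BCVA: recorded as logMAR on ETDRS charts, with no size of loss named as worsening.
- Slit lamp: normal or abnormal with an explanation, and no rule for stability.
- Fundus: includes optic nerve pallor and cupping, and no rule for stability.
- Section 9.4.4: summary statistics, with no rule for a conclusion.

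**The case against.** The strongest reply is that this is one over-confident sentence in a plan that is otherwise candid. The study is a pilot, disclaims power in both documents and summarises safety descriptively, and no decision rule depends on 9.1. That stands, and it limits the severity. It does not rescue the sentence, because a study that disclaims power should not also promise a demonstration.

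A reader might infer four stronger points that the documents do not support:

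- **A non-significant p-value will be read as safety.** Neither document says so. The SAP names no variables, so the t test may not be meant for IOP at all. It also plans 95% intervals, which would show what size of change cannot be excluded.
- **Treated participants who withdraw are left out of the safety analysis.** Section 9.4.3 already assigns IOP to the safety population, and 9.3 describes such a dataset. The SAP says its analysis includes completers, which is not clearly exclusive. What stands is that the two documents need aligning, since section 7.2 has treated participants who withdraw replaced.
- **Individual harm would go unrecorded.** Sections 7.1 and 8.3.4 make new clinically relevant findings, and deterioration of existing conditions, adverse events. Section 7.1 requires all four eye assessments when treatment is discontinued. Section 9.4.4 adds: "Adverse events leading to premature discontinuation from the study and serious treatment-emergent AEs will be presented separately in a listing". These safeguards capture events, but they do not define no change.
- **Corneal stability cannot be judged because entry requires corneal staining.** Those stains are counted separately under fluorescein (sections 1.3 and 8.1), so that abnormality has its own numeric measure.

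Nor is a mean-IOP claim impossible in 12 people. With a small SD and a wide enough margin fixed in advance, an interval could support it. The plan fixes no margin.

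**Conclusion.** The point holds as a mismatch between the conclusion promised in 9.1 and what the design and analysis can deliver. It is minor to moderate: it affects what the trial may claim about safety, not how participants are monitored.

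The firmest number is the 26% upper limit for 0 of 12, which rests only on n = 12 and independent participants. The 12%, 44% and 65% figures depend on the assumed SDs and the assumed 2 mm Hg rise, and apply only if the SAP's t test is used for IOP. The wide range shows that an unknown SD decides how reassuring a non-significant result would be. The undefined terms for BCVA and the examinations are missing detail that adds to the main point.

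**What to change.** **Protocol 9.1.** Replace the safety sentence with a statement that the study will estimate change in IOP, BCVA, slit lamp and dilated fundus findings.

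**SAP.** Add a short safety paragraph:

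1. Analyse these measures in all treated participants, as 9.4.3 already says for IOP, and not in completers only. Include those who withdraw and are replaced, using the section 7.1 discontinuation examination.
2. Report mean IOP change and mean logMAR change with 95% confidence intervals.
3. Report the number of participants with the plan's 10 mm Hg IOP increase, and the numbers with new or worsened slit lamp or fundus findings, each with an exact 95% interval. State how two eyes are counted.
4. State that a non-significant p-value will not be interpreted as no change.
5. If a no-change claim is kept for any measure, fix its margin and interval rule before the data are seen.

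**Cost.** One sentence in the protocol, one paragraph in the SAP and a little more analysis work. The examinations are already planned and no extra participants are needed. The real price is a less favourable safety statement.

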9.2 SAMPLE SIZE DETERMINATION

This is a small pilot study of 12 participants completing the study assessments. There is no placebo and it is not powered to show statistical significance.

9.3 POPULATIONS FOR ANALYSES

- *Intention-to-Treat (ITT) Analysis Dataset (i.e., all randomized participants)*
- *Safety Analysis Dataset: defines the subset of participants for whom safety analyses will be conducted (e.g., participants who took at least one dose of study intervention)*

9.4 STATISTICAL ANALYSES

9.4.1 GENERAL APPROACH

As a guide, the following should be addressed, as appropriate:

- *Categorical and continuous data will be presented as percentages, means with standard deviations, median, and range).*

9.4.2 ANALYSIS OF THE PRIMARY EFFICACY ENDPOINT(S)

For each primary endpoint:

The improvement of patient comfort as measured by the dry eye comfort questionnaire OSDI defined as the mark listed in mm by the patient describing sensation of dryness. It will be measured at each study visit and reported as an ordinal endpoint. Descriptive statistics will be used for intent to treat patients and safety populations who receive at least one dose of the study drug.

- *The improvement of corneal staining after fluorescein instillation in which discrete superficial punctate stains are counted.. Descriptive statistics will be used for intent to treat patients and safety populations who receive at least one dose of the study drug.*
- *Missing data will be handled by imputation. Outliers will be evaluated by the primary investigator. Subjects who are nonadherent will be referred for re-training and those lost to follow up will be contacted by the study coordinator at least 3 times by phone and ultimately with certified letter if telephone contacts are unsuccessful.*

9.4.3 ANALYSIS OF THE SECONDARY ENDPOINT(S)

For each secondary endpoint:

- *The improvement of conjunctival staining after lissamine green instillation in which discrete superficial punctate stains are counted.. Descriptive statistics will be used for intent to treat patients and safety populations who receive at least one dose of the study drug.*
- *IOPs will be analyzed for mm Hg increase from baseline, also noting 10 mm Hg increase from baseline. It will be measured at each visit. Descriptive statistics will be used for intent to treat patients and safety populations who receive at least one dose of the study drug.*

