1.3 SCHEDULE OF ACTIVITIES (SOA)

u

Procedures	Screening Day -7 to -1	Enrollment/Baseline Visit 1, Day 1	Study Visit 2 Day 7 +/-1 day	Study Visit 3 Day 14 +/-1 day	Final Study Visit 13 Day 84 +/-1 day
Informed consent	X				
Demographics	X				
Medical history	X				
Randomization	X				
Administer study intervention		X			
Concomitant medication review	X	X----- -----X			
Bcva	X	X	x	x	X
Slit lamp biomicroscopy	X	x	x	x	x
IOP	X	X	x	X	X
Corneal fluorescein stain	X	X		X	X
Conjunctival liissamine stain	X	X		X	X
	X	X		X	X
anesthetized schirmer	X	X		x	x
Dilated ophthalmoscopy	X				x
Training on study medications	X				
Dispense study meds					
\	X				

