6.1.2 DOSING AND ADMINISTRATION

Each participant will be started at 80 IU subcutaneously 2-3 weekly and the dosing increased to up to three times weekly at the discretion of the primary investigator. The dosing will remain consistent unless the investigator decides to reduce or escalate the dosing at the one month mark. The dosing may be stopped altogether and the subject followed only for safety in the event of uncontrolled hypertension, blood sugar, glaucoma or other serious adverse events in the opinion of the investigator. The dosing of study drug will continue for 12 weeks.

Missed or delayed doses should be taken as soon as realized unless it would result in two doses being given at once, in which case the investigator should be contacted for a modified dosing schedule.

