6.5 CONCOMITANT THERAPY

For this protocol, a prescription medication is defined as a medication that can be prescribed only by a properly authorized/licensed clinician. Medications to be reported in the Case Report Form (CRF) are concomitant prescription medications, over-the-counter medications and supplements.

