8.2 SAFETY AND OTHER ASSESSMENTS

- **BCVA Subjects will be placed at the predetermined mark for ETDRS testing**
- **LogMAR will be assessed with ETDRS or modified ETDRS charts and with subjects own corrective lenses or BCVA measured in office whichever is better. Scores are recorded according to ETDRS protocol and right eyes tested first.**
- **Slit lamp biomicroscopy – 8 mm x 2 mm slit lamp beam will be used right to left and left to right to examine thoroughly the structures of the anterior segment: lids, lashes, conjunctiva, cornea, iris, anterior chamber, and lens. Results will be recorded as normal or abnormal. Abnormal findings will be followed by explanation of pathology.**
- **IOP measurements will be performed using Goldman applanation tonometry according to the investigators standard protocol. All pressures will be recorded in mm Hg. IOP will be measured at each time point and at the investigator's discretion.**
- **Dilated ophthalmoscopy will occur at the first and last study visit and include assessment of the optic nerve head for pallor and cupping.**

Adverse events will be collected at each time point

h

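### A treated eye-pressure rise, or one that ends participation, can drop out of the baseline-to-final IOP comparison and support a conclusion of no change; other parts of the plan offset this only in part

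*Protocol*

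**What the plan says.** The IOP hypothesis is in Protocol 9.1: "The study will demonstrate no change in baseline to final intraocular pressure". It compares two time points.

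Protocol 9.4.3 gives the analysis: "IOPs will be analyzed for mm Hg increase from baseline, also noting 10 mm Hg increase from baseline". It adds "It will be measured at each visit" and names the intention-to-treat and safety populations, that is, everyone dosed. Section 8.2 provides for readings outside the schedule as well: "IOP will be measured at each time point and at the investigator's discretion".

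The SAP is one paragraph and names no endpoint. It covers participants who complete the trial, and change from baseline to final visit together with changes between visits.

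Four other provisions matter:
- Section 6.1.2 lets dosing stop, with safety follow-up only, "in the event of uncontrolled hypertension, blood sugar, glaucoma or other serious adverse events in the opinion of the investigator".
- Section 6.5.1 allows rescue medication at any time and has it recorded. Section 6.5 covers the rest: "Medications to be reported in the Case Report Form (CRF) are concomitant prescription medications, over-the-counter medications and supplements".
- Section 7.2 has treated participants who later withdraw replaced, and 9.2 sets the size at 12 who complete.
- Section 9.4.8 rules out listing individual data by measure and time point.

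**The concern.** Section 2.3.1 lists glaucoma as a known risk of the drug, and Section 3 gives glaucoma as one reason for the safety measurements. A meaningful pressure rise can lead to pressure-lowering treatment, to stopping study drug, or to leaving the study. After treatment or stopping, the Day 84 pressure no longer describes continued exposure to study drug alone. After leaving, there may be no Day 84 pressure at all. The plan gives no rule for IOP values after any of these events.

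The hypothesis rests on the comparison most exposed to this. The more effectively rises are dealt with during the study, the closer the final mean change moves to zero. A statement of no change could then partly reflect the response to the rises rather than their absence.

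**Working it through.** The documents give no IOP event rate or standard deviation, so there is no planned figure to reproduce. The check sets the provisions side by side and then illustrates the size.

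**1. Where each kind of rise would appear**

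- *Rise of 10 mm Hg or more, treated, participant stays.* It is missing from the baseline-to-final change if pressure has returned. The 10 mm Hg note in 9.4.3 should catch it if it is seen at a visit. The note does not say that one reading at any time is enough, does not name the eye, and does not mention the discretionary readings in 8.2.
- *Smaller rise, treated, participant stays.* It is missing from the final change and is not flagged. It may show in a by-visit mean or range, if a visit falls while pressure is raised.
- *Study drug stopped, participant stays.* The final value is off drug but enters the comparison unmarked. The separate listing in 9.4.4 covers serious events and events leading to departure from the study. Section 7.1 treats stopping drug as a different thing.
- *Participant leaves.* They are in the 9.4.3 populations but not among the SAP's completers, and 7.2 has them replaced.

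**2. Mean change when the participant stays**

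Inputs: n = 12 (Protocol 9.2). The number affected (k), the size of the rise and the return to baseline by Day 84 are assumed. Mean change at the peak = k × rise / 12, if the peaks share a visit and the other participants do not change.

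| Assumed rise | Mean at peak (mm Hg) | Mean at final visit | Flag counted at any reading |
|---|---|---|---|
| 1 of 12, 10 mm Hg | 1 × 10 / 12 = +0.83 | 0.00 | 1/12 = 8.3% |
| 2 of 12, 10 mm Hg | 2 × 10 / 12 = +1.67 | 0.00 | 2/12 = 16.7% |
| 3 of 12, 10 mm Hg | 3 × 10 / 12 = +2.50 | 0.00 | 3/12 = 25.0% |
| 2 of 12, 8 mm Hg | 2 × 8 / 12 = +1.33 | 0.00 | 0/12 |

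If pressure returns only to 2 mm Hg above baseline, the final mean for 1 to 3 affected participants is 1 × 2 / 12 = +0.17 to 3 × 2 / 12 = +0.50 mm Hg. In the last row the 10 mm Hg flag shows nothing however it is read. A count of participants who started pressure-lowering treatment would show 2/12 = 16.7%.

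**3. Counts when the participant leaves and is replaced**

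Suppose w dosed participants leave after a 10 mm Hg rise, each is replaced, and nobody else leaves or has a rise. Completers show 0/12. Everyone dosed shows w / (12 + w): 1/13 = 7.7%, 2/14 = 14.3% or 3/15 = 20.0% for w = 1, 2 or 3.

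**The case against.** The strongest reply is that IOP is not judged at the final visit alone. Section 9.4.3 does not restrict the analysis to that visit, and it has its own 10 mm Hg note and a population of everyone dosed. The SAP adds changes between visits. Section 9.4.1 calls for medians and ranges, so a large rise at a visit would show as an extreme value. Section 7.1 makes any new clinically relevant finding an adverse event, 8.3.4 has all events documented whatever their cause, and 9.4.4 counts each once per participant. A rise serious enough to be treated should appear there.

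All of that stands. A reader might infer that a treated rise would be reported as no change by the plan as a whole, and the documents do not support that. Nor do they support inferring that anyone stopped for glaucoma is lost from the analysis. Section 7.1 asks for remaining procedures to be completed after drug is stopped and collects IOP at that point, so someone who attends the last visit counts as a completer under 4.4.

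Two further limits apply. No provision says that pressure would be back at baseline by Day 84; the illustration assumes it. The schedule in 1.3 as available shows no column between Day 14 and "Final Study Visit 13 Day 84 +/-1 day", but the visit number suggests that columns were lost in the text. The point does not rely on a gap in visits.

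The reply does not close the gap. Adverse events are not linked to the IOP analysis, smaller treated rises are not flagged, and without individual listings a reader cannot recover a participant's course. The small, unpowered, descriptive design limits what any IOP summary can show, but it does not make the final-visit comparison a better one.

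**Conclusion.** The point holds for the baseline-to-final comparison on which the IOP hypothesis rests. A rise followed by pressure-lowering treatment, by stopping study drug or by withdrawal could be missing from that comparison and support a no-change conclusion. The 10 mm Hg note, the by-visit summaries and adverse event reporting are partial safeguards.

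Under the assumed full return to baseline, the final mean understates the peak by 0.83 to 2.50 mm Hg when 1 to 3 of 12 participants rise by 10 mm Hg. Under the assumed withdrawals with replacement, a completers-only count shows 0% where the dosed population shows 7.7% to 20.0%. These figures show the mechanism and do not predict what will happen. The conflict between the SAP's completers and the populations in 9.4.3 is in the text and needs no assumption.

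This should be corrected before analysis. It affects how IOP safety is reported and does not undermine the trial's other measures.

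**What to change.** In Protocol 9.1 and 9.4.3 and in the SAP:
- Analyse IOP in all participants who received study drug, so that the SAP agrees with 9.4.3.
- Define the 10 mm Hg flag as reached at any post-baseline reading, scheduled or unscheduled, in either eye.
- Report each participant's maximum post-baseline change (worse eye) beside the final-visit change.
- Tabulate participants who started or increased IOP-lowering medication, and those whose study drug was stopped for pressure or glaucoma.
- Flag final values taken after either event.

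IOP readings and concomitant medications are already collected. Section 7.2 records the reason for leaving the study, but the data listed in 7.1 do not include the reason for stopping drug alone, so one CRF field may be needed. The other cost is that the maximum-change summary will look less favourable than the final-visit mean. These are reporting changes only; no rule for managing a pressure rise is proposed.
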